**COMPLIANCE AND SAFETY MONITORING:**

Monitoring and Managing Adherence to Treatment:

Pill/Sachet counts and/or review of the medication log will be used to estimate compliance, along with queries about missed doses. We will require a standard of four days out of seven on treatment to obtain a rating but will counsel the participant and family about the importance of adherence in such a situation. We will require a minimum of 5 days per week on treatment in each of the final two weeks of each treatment block, so that the end-of-treatment ratings are an accurate reflection of treatment. For the final study visit and pTMS assessment, subjects must have 100% compliance for the two days prior to testing or testing will be rescheduled within a reasonable 3-4 day window so that compliance can be assured.

Communication:

To facilitate data collection, safety monitoring, and accommodate preferences of participants, communication between study staff and the research participant/family/teachers will utilize a variety of technologies. Modes of communication may include phone calls, videoconference, electronic mail (e-mail), REDCap surveys (via e-mail link or Twilio text message), and in person meetings. Responses to safety assessments will be reviewed by a member of the study team within 48 hours. As described elsewhere, if a participant/family discloses any suicide ideation or significant health concerns at any point in this study, the study staff will contact the participant's mental health provider or primary care provider and/or Psychiatric Intake Response Center (PIRC) at CCHMC for further assessment and guidance within 24 hours.

Video recordings may aide recruitment and explanation of study assessments/details. These recordings may be distributed in a similar manner to other advertisements (websites, philanthropic/educational events, through interactions related to clinic visits, distributed via REDCap correspondence, et cetera). Examples or video content would be a short description of TMS and PANESS procedures. A general outline of the study (risks/benefits, procedures, timeline, et cetera) as would be described during informed consent would also be advantageous.

Medical/safety assessments:

During screening, children will receive a review of systems and physical examination, laboratory measures (CBC, basic chemistries with liver transaminase, thyroid function test, urinalysis), and pregnancy test (if relevant). Pregnancy tests will be administered when deemed appropriate by the study doctor or designee. Results of the pregnancy test will be provided to the parent/guardian of the participant. If an uninterpretable urine pregnancy test is obtained or if the participant cannot/refuses to provide a urine sample, then a serum pregnancy test will be performed. All values outside the reference range will be assessed by the investigator, [name], for clinical relevance.

All MRI's will undergo a safety review by a radiologist in order to determine whether there are any clinically relevant incidental findings that require referral for appropriate clinical follow-up. Referrals for clinical follow-up will be provided and that an individual with appropriate clinical qualifications will inform the research subjects of the need for the clinical follow-up.

Measurement and Management of Adverse Effects:

Participants and parents/guardians will be given the opportunity to report AEs to the investigator spontaneously in response to a general prompt (e.g. "Any changes in your health since the last visit?"). Terminology for adverse events (AEs) will follow the Medical Dictionary for Regulatory Activities (MedDRA) version 20.1 (<https://www.meddra.org>) (Table 6). If AEs occur, the investigator will rate the seriousness of the event, whether the event was anticipated, and the likelihood that it is related to NAC. Serious events will be reported to the IRB within 24 hours of awareness. All other adverse events will be reviewed quarterly by the study team.

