### **STUDY DESIGN:**

This is a prospective single-center; randomized, double-blind, placebo-controlled Phase II study to determine the safety and efficacy of NAC on motor behavior and/or attention deficits of children with NF1 aged 8 to 16 years. Participants will be randomized to 8-weeks of treatment with NAC (70 mg/kg/day) versus placebo. This is a collaborative study between multiple specialties at CCHMC and external collaborators at Children’s National Hospital and Technion Israel Institute of Technology. We have received IND approval from the FDA to use NAC for the application in this study (IND# 139468).

It is plausible and ethical to employ a placebo group, as no standard therapy with established efficacy is being withheld. There is no crossover in this study due to a lack of data concerning the length of possible washout effects. Primary and secondary outcome measures will be administered at baseline, after 8 weeks of treatment and at follow-up, 4 weeks after cessation of treatment to determine any washout effects.

In addition, the effect of NAC on measures of impulsivity, attention, executive function, and SICI and imaging biomarkers will be assessed. Participants will be carefully monitored for side effects by a medical safety monitor for the study. The safety of NAC will be evaluated using laboratory tests, clinical signs and adverse effects, which will be monitored at regular intervals over the 8-week treatment period.

An additional cohort of age/sex-matched NF1 participants will be recruited in order to characterize and validate biomarkers of brain function.

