#### **PARTICIPANT WITHDRAWAL**

A participant may withdraw from the study at any time. Participants considering withdrawal should contact the investigator so that the investigator can help you with a plan to stop the study drug safely.

The person in charge of the research study or the sponsor can remove participants from the research study without their approval. Possible reasons for removal include:

1. Adverse events requiring removal from protocol therapy
2. Inability or refusal to continue the study by patient/parent/guardian
3. Physician determines it is in patient's best interest

In the case of participant withdrawal/removal, data already collected may not be removed from the study database. The study team will request permission to collect data from your routine medical care. If the participant agrees, this data will be handled the same as research data.

The study team will inform the participant about any new information that may affect health, welfare, or choice to stay in the research.

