## **STUDY PROCEDURES:**

### **Study Variables and Measurements - Overview:**

We propose to study all measurements at baseline, 8 weeks after treatment, and 4-week post-treatment (washout period) to assess for carry-over effects. We will compare PANESS and SICI measures in 58 children with NF1 to data already acquired at CCHMC for those 2 measures (**Figure 14**). Next, these children will be treated with NAC (n=29) or placebo (n=29) as described above (**Figure 16**).

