For analyses of change over time, mixed models which include subject-specific random effects will be used to account for the correlation of multiple measurements on each subject and capture between-subject variation in rates of change. Unless otherwise noted, the Type I error rate for hypothesis tests and confidence intervals will be controlled at  $\alpha=0.05$ . To assist interpretation, the size of effects of interest in each model will be represented by  $R^2$  (proportion of outcome variation explained by predictors) for linear regression models and/or Cohen's  $d$  (difference in group means, in standard deviation units) for two sample t-tests [81].

Exploratory and descriptive data analysis will precede all inferential analyses to ensure that distributional assumptions are satisfied. In addition to computation of basic descriptive sample statistics (measures of central tendency, variability, and bivariate association), graphical tools such as histograms and scatterplots will be used to assess, e.g., approximate normality, linearity, and presence of influential outlying observations. If substantial violations of parametric assumptions are detected, we will implement non-parametric alternatives, including classical rank-based procedures as well as computationally-intensive sample re-use procedures such as the nonparametric bootstrap. Non-parametric procedures generally have less power than parametric procedures when the assumptions of the latter are met, but often have markedly better properties when the assumptions fail.

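### The adherence standards can be read as withholding the week-8 PANESS from less adherent children, and the analysis text supplied has no as-randomised rule to settle it

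*Combined protocol and SAP*

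**What the plan says.** The adherence paragraph under Compliance and Safety Monitoring sets three rules.

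- **Four days in seven.** "We will require a standard of four days out of seven on treatment to obtain a rating". The same sentence goes on to say that the family will be counselled in that situation, so it is unclear whether the rating still takes place.
- **Five days a week at the end of treatment.** The plan requires a "minimum of 5 days per week on treatment in each of the final two weeks of each treatment block", so that the end-of-treatment ratings reflect treatment. No consequence of falling short is given.
- **Full compliance for the two days before testing.** If this is missed, "testing will be rescheduled within a reasonable 3-4 day window". This is the only rule with a stated action. Nothing covers a child who still falls short after rescheduling.

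The schedule has no such condition. Under Study Design, "Primary and secondary outcome measures will be administered at baseline, after 8 weeks of treatment and at follow-up". The procedures overview likewise lists all measurements at these times, and Table 4 marks PANESS at weeks 1, 8 and 12 without an adherence footnote.

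Under Statistical Analysis, for change over time, "mixed models which include subject-specific random effects will be used". The missing-data paragraph is written for children lost to follow-up, under missing at random. Its sensitivity analysis, which carries the last observation forward, requires at least one dose. Neither that paragraph nor the sample-size section defines an as-randomised set or a per-protocol set. Some text directly after the statistical section was not available for review, so these absences are judged on the text supplied.

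**The concern.** Two staff members could follow the adherence paragraph and treat the same child differently at the primary endpoint. PANESS has no on-treatment value before week 8, so a child not rated then contributes a baseline and at most a week-12 value taken four weeks off drug.

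Adherence is a post-randomisation variable and may depend on tolerability. The risk section lists nausea, vomiting and diarrhoea among the common side effects of NAC, and Table 8 provides for interrupting treatment. An interruption matters here only if it leaves the child below standard near week 8. If children are left out on this basis, the week-8 result describes adherent children only. The comparison between arms is biased if the unrated share, or its link to outcome, differs by arm. Withheld ratings also reduce a sample that was enlarged for dropout alone.

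**Working it through.** **1. The two readings.** If the four-day rule is a real gate, it is at odds with the unconditional week-8 assessment in Study Design, the procedures overview and Table 4. If it means rated and counselled, nothing conflicts, but the purpose of the standard and its place in the analysis are undefined. The five-day rule lacks a consequence on either reading.

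**2. The plan's own figures.** Inputs from the sample-size section: two-sided t-test, 26 per arm, effect 0.8 SD, alpha 0.05, 10% dropout. Noncentral-t power is 80.7% (stated 81%). Enrolment is 52/0.9 = 57.8, rounded up to 58. Both reproduce. There is almost no slack: 58 × 0.9 = 52.2 against 52 needed.

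**3. Power if ratings are withheld in both arms.** The documents give no non-adherence rate, so the share x is assumed. Rated per arm = 26 × (1 − x), effect kept at 0.8 SD.

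| x | Rated per arm | Power |
|---|---|---|
| 5% | 24.7 | 78.6% |
| 10% | 23.4 | 76.3% |
| 20% | 20.8 | 71.1% |

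**4. Bias if the arms differ, with no true effect.** Assume that latent adherence is standard normal and has correlation r (0.3 to 0.7) with the week-8 change, and that the lowest share q of an arm goes unrated. The mean change in the rated children shifts by r × φ(z_q)/(1 − q), in SD of change:

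- q = 5%: 0.103/0.95 = 0.109
- q = 10%: 0.1755/0.90 = 0.195
- q = 20%: 0.280/0.80 = 0.350

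Bias of a rated-only comparison:

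- 20% v 5%: r × (0.350 − 0.109) = r × 0.241, or 0.07, 0.12 and 0.17 at r = 0.3, 0.5 and 0.7.
- 10% v 5%: r × 0.086, or 0.03, 0.04 and 0.06.

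The sign follows the assumed sign of r.

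**5. Type I error.** Null simulation with 29 per arm, 20,000 trials per scenario and an assumed within-child correlation of 0.7. The analyses are a t-test on rated children and a random-intercept mixed model with the week-12 value either obtained or also missing. Ranges are over r = 0.3 to 0.7.

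| Unrated share | t-test | Mixed model, week 12 obtained | Mixed model, week 12 missing |
|---|---|---|---|
| 10% v 10% | 4.9–5.3% | 4.2–4.8% | 4.1–4.9% |
| 20% v 20% | 4.9–5.1% | 3.6–4.7% | 3.7–4.9% |
| 10% v 5% | 5.3–5.9% | 4.7–5.0% | 4.6–5.0% |
| 20% v 5% | 5.7–9.3% | 5.1–6.1% | 5.5–7.2% |

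At 20% v 5% the mixed model lowers the bias to 0.05–0.12 SD (week 12 obtained) or 0.06–0.14 SD (week 12 missing).

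**6. Rating everyone instead.** Suppose a share q of NAC children is non-adherent and keeps a fraction k of the effect. The effect in all randomised children is 0.8 × ((1 − q) + q × k). Power is at 26 per arm, against the gated figures in step 3.

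| q | k | Effect (SD) | Power, all rated | Power, gated |
|---|---|---|---|---|
| 10% | 0 | 0.72 | 72.1% | 76.3% |
| 10% | 0.5 | 0.76 | 76.6% | 76.3% |
| 20% | 0 | 0.64 | 61.9% | 71.1% |
| 20% | 0.5 | 0.72 | 72.1% | 71.1% |

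**The case against.** A reader might infer that the protocol flatly contradicts itself. The documents do not support that. The four-day sentence is an ambiguous gate, and the conflict exists only on its literal reading. The five-day sentence, which is the one about end-of-treatment ratings, mentions no withholding. A schedule without a condition is also weak evidence on its own: Table 4 lists the pregnancy test without the discretion that the safety section allows. This part of the objection stands.

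The plan also works to keep adherence up. There is a placebo test dose at screening, medication-log review at weeks 2, 4, 6 and 8, pill or sachet counts, questions about missed doses, counselling, and rescheduling before testing. This suggests an intent to correct adherence and obtain the rating. It lowers the likely number of unrated children but does not say what happens to those who remain below standard.

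Finally, an exploratory phase II trial may reasonably want an on-treatment effect. That is a fair aim, but comparing the adherent children in each arm is not a randomised comparison. A per-protocol sensitivity set serves the aim without giving up the primary one.

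**Conclusion.** The point holds as an ambiguous rule that should be fixed. On its literal reading it withholds the only on-treatment primary measurement on a post-randomisation basis; on the other reading the handling is undefined. The analysis text supplied does not repair either.

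The likely size is modest and rests on assumed shares and correlations. At 20% v 5% unrated, bias is 0.05–0.17 SD and type I error 5–9%, depending on the analysis. At 10% v 5% the error is 5–6%, and with equal shares it is about 5% or below. The power cost needs no imbalance: about 76% or 71% with a further 10% or 20% unrated in both arms.

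Two stronger inferences fail. One is that the trial's result will be biased: the documents give no non-adherence rate, no imbalance and no link to outcome, so neither size nor direction can be derived. The other is that rating everyone lowers power from 81% to 72%. That compares a diluted effect with a gated design that still has 26 rated per arm. On equal terms at 10%, the difference is about 4 points, or about none if non-adherent children keep half the effect.

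**What to change.** Reconcile the adherence paragraph with Study Design, the procedures overview and Table 4 by stating that:

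- the week-8 PANESS and the other outcome ratings are obtained from every randomised child whatever the adherence, unless consent to assessment is withdrawn;
- the primary analysis is by randomised group;
- the four-day and five-day standards serve only to define a per-protocol sensitivity set;
- the rescheduling window may stay, but failing it does not remove the child's rating.

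Secondary wording should be settled at the same time. The withdrawal section allows removal from the research for "Adverse events requiring removal from protocol therapy", after which it says only "The study team will request permission to collect data from your routine medical care"; coming off study drug should be separated from leaving assessments. The references to repeated treatment blocks and to compliance before the final study visit do not fit a single 8-week treatment period followed by an off-drug Visit 4.

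The cost is protocol wording, since the visits are already scheduled. The downside is possible dilution of the estimated effect. If non-adherent NAC children gain nothing, power is about 4 points below gating at 10% non-adherence (72.1% v 76.3%) and about 9 points below at 20% (61.9% v 71.1%). If they keep half the effect there is essentially no loss.

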**Table 4: Schedule of Assessments**

	Visit 1	Visit 2				Visit 3		Visit 4
	Screening	Baseline	Abbreviated Remote monitor and safety	Remote monitor and safety	Abbreviated Remote monitor and safety	End Intervention	Remote monitor and safety	Follow Up
Task	Week 0	Week 1	Week 2	Week 4	Week 6	Week 8	Week 10	Week 12
Review Eligibility Criteria $\Psi$	X							
KBIT-2 (Kaufman Brief Intelligence Test, Second Edition) $\Psi$	X							
KSADS (MedHis)	X							
Cognitive Function Screening $\Psi$	X							
Test dose	X							
Informed Consent $\Psi$	X							
Brain Imaging (MRI/MRS) $\Psi$		X				X		X
Urine Pregnancy (Females only)	X	X						
Vitals*		X				X		X
Safety labs*		X				X		X
Physical Exam*		X				X		X
ADHD-RS (DuPaul) $\Psi$		X		X		X	X	X
KSADS (CC)		X		X		X	X	X
PARS (Pediatric anxiety rating scale)		X		X		X	X	X
CDRS (Children's depression rating scale)	X	X		X		X	X	X
C-SSRS (Columbia Suicide Severity Rating Scale)	X	X		X		X	X	X
Wechsler Intelligence Scale for Children, Fifth Edition (WISC-V) $\Psi$	X	X				X		X
Behavioral Rating Inventory of Executive Function (BRIEF-2) $\Psi$		X				X		X
Test of Variables of Attention (TOVA) $\Psi$		X				X		X
PANESS scale $\Psi$		X				X		X
TMS assessment $\Psi$		X				X		X
NAC/Placebo Prescription		X						
Med Log		X	X	X	X	X	X	X
AE assessment (MedDRA)		X	X	X	X	X	X	X
Follow-up plan								X

\* Indicates clinical procedures performed as standard of care

$\Psi$  Indicates research procedures to be completed in both treatment and non-treatment cohorts

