**Determination of sample size:**

No data exist on the effects of NAC in children with NF1. Clinical improvement will be evaluated as a change score ( $\text{PANESS}_{\text{post-NAC}} - \text{PANESS}_{\text{baseline}}$ ). Those subjects whose severity PANESS score decreased by at least 20% from baseline to week 8 will be considered clinically meaningful. The sample size calculation was based on a two-sided t-test to detect the difference in change scores between two groups. We assume the PANESS score does not change for patients in placebo group. A sample size of 26 participants per group (52 in total) achieves 81% power to detect an effect size of 0.8 with significance level of 0.05 [80]. To allow for a 10% dropout rate prior to the 12-week point, a total of 58 participants will be enrolled.

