**COST OF PARTICIPATION:**

There will be no charges to participants or to third party payers related to study visits or procedures in this study. NAC is an FDA approved medication. NAC will be provided for the 8 week duration of the study to all participants.

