**COMPENSATION/PAYMENT FOR PARTICIPATION:**

Families will be compensated for time, effort, and travel as described in the table below. For the first 3 study visits, each participant will receive \$25. Study visit 4 has additional conditions (i.e.: return of drug diary and unused drug), therefore, each participant will receive \$100 for that visit. Total compensation for this study per participant is \$175. Reimbursement will be distributed within 90 days of study completion or withdrawal.

Payment Schedule			
Visit 1 $\psi$	Visit 2	Visit 3	Visit 4
\$25	\$25	\$25	\$100

$\psi$  Indicates treatment- and non-treatment cohort payment

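### The two-day full-compliance rule is attached to the final visit, which is 4 weeks off drug, and does not name Visit 3 (Week 8), where the primary PANESS change is measured

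*Combined protocol and SAP*

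**What the plan says.** COMPLIANCE AND SAFETY MONITORING sets three adherence rules:

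- A child needs four days in seven on treatment for a rating to be taken.
- In each of the last two weeks of every treatment block the minimum is five days per week. The stated purpose is that end-of-treatment ratings should reflect treatment.
- "For the final study visit and pTMS assessment, subjects must have 100% compliance for the two days prior to testing". If this is not met, testing is moved within a window of 3-4 days.

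The visits are set elsewhere. STUDY DESIGN has outcomes measured at baseline, "after 8 weeks of treatment and at follow-up, 4 weeks after cessation of treatment to determine any washout effects", and adds: "There is no crossover in this study". In Table 4, Visit 3 (Week 8) is headed "End Intervention". Visit 4 (Week 12) is the follow-up visit and the last one listed. PANESS and TMS are both marked at Visits 2, 3 and 4. On supply, COST OF PARTICIPATION says: "NAC will be provided for the 8 week duration of the study to all participants".

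Determination of sample size treats a child as meaningfully improved if the PANESS score "decreased by at least 20% from baseline to week 8 will be considered clinically meaningful". Statistical analysis uses two-month changes in PANESS, SICI, FA, GSH and GABA, and adds: "For analyses of change over time, mixed models which include subject-specific random effects will be used".

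On drug return, COMPENSATION/PAYMENT FOR PARTICIPATION says: "Study visit 4 has additional conditions (i.e.: return of drug diary and unused drug", with $100 paid for that visit. Table 4 marks a Med Log at Weeks 8, 10 and 12, among others.

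**The concern.** The rule exists so that a child is tested while reliably on drug. Its wording points to the one post-baseline visit at which every child is meant to be off drug. Visit 3 is where recent dosing matters, because the primary PANESS change and the two-month TMS and imaging changes all come from it. No section applies the two-day rule to Visit 3 by name. The reference to more than one treatment block in the preceding sentence has a similar problem, since each child has a single treatment period.

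Two things are at stake. The first is whether staff apply the two-day check and the rescheduling at Week 8. The second is smaller and concerns Week 12 only. The one stated point for returning unused drug is Visit 4, and no visit is named for the pill or sachet counts, so leftover drug may stay at home through the washout. Leftover NAC is active and leftover placebo is not. Any dosing after Visit 3 would therefore make a treatment effect look more persistent at Week 12, and would carry into any mixed model that uses those data.

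**Working it through.** **The plan's own figures.** With 26 per group, an effect size of 0.8 and two-sided alpha of 0.05, the noncentral t calculation gives 80.7% power (stated: 81%). For dropout, 52 / (1 - 0.10) = 57.8, rounded up to 58 (stated: 58). Both reproduce. Neither contains an adherence term, so the wording of the compliance rule does not enter them.

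**Where the rule can operate.** TMS and PANESS are done at three visits:

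- Visit 2, baseline: before any study drug.
- Visit 3, Week 8: end of treatment, with the child on drug in the preceding days.
- Visit 4, Week 12: 12 - 8 = 4 weeks, or 28 days, after treatment stops.

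A requirement for full dosing on the two preceding days can be met only at Visit 3. At Visit 4, a 3-4 day postponement moves testing from day 28 to day 28 + 3 = 31 or 28 + 4 = 32 off drug, with the requirement still unmet.

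**What is left at Week 8 if the rule is read literally.** The 5-of-7 standard permits 7 - 5 = 2 missed days in the last week, which is 2 x 2 = 4 doses at twice-daily dosing (Table 3). Nothing stops these from being the last two days. The following assumes that missed days are equally likely to fall on any of the seven days before the test:

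- One missed day: P(it is one of the last two) = 2/7 = 29%.
- Two missed days: P(at least one is in the last two) = 1 - C(5,2)/C(7,2) = 1 - 10/21 = 52%.
- Two missed days: P(both are the last two) = 1/21 = 5%.

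These are conditional on a child having already missed exactly one or two days that week. The documents do not say how often that happens.

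**Leftover drug, as an illustration only.** Assume full dose, 56 dosing days and no overage in the kit. At 90% adherence, 56 x 0.10 = 5.6, about 6 days' supply, remains. At 80%, 56 x 0.20 = 11.2, about 11 days' supply, remains.

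**The case against.** The strongest reply is that this is a slip in a label with only one workable reading. The sentence sits under a heading on adherence to treatment and follows a rule about end-of-treatment ratings. A dosing rule cannot operate a month after the drug stops, so sensible staff would apply it at Visit 3. That stands: Visit 3 is the evident intent, and some staff may already work that way. It does not remove the need to name the visit, because the sentence triggers rescheduling of a test and should be workable as written.

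The reference to the pTMS assessment could also be taken to cover every TMS session, which would bring in Week 8. That reading is possible but less natural, since the word final most readily governs both nouns. Even so, it would not name the Week 8 PANESS.

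A reader might infer that Week 8 has no adherence control. It does: the 5-of-7 and 4-of-7 standards still apply, and only the two-day requirement is missing. A reader might also infer a loss of power or a bias in the primary comparison. The documents give no link between two missed days after eight weeks of dosing and the PANESS score, so no such loss can be claimed.

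On leftover drug, one might apply 4-of-7 to six weeks and 5-of-7 to two, giving 56 - (6 x 4 + 2 x 5) = 22 days, and call that a maximum. It is not a bound. The 4-of-7 standard is only a condition for taking a rating, and the Dose Modification section allows interruption and halving. The $100 tied to Visit 4 and the Med Log contacts at Weeks 10 and 12 also give some protection. They could detect later dosing, but they do not take the drug out of the home.

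**Conclusion.** The point holds as a defect in an operative rule. As written, the two-day requirement is tied to a visit where it cannot be met, and the visit it evidently serves is not named. Read literally, the Week 8 PANESS and TMS visit has only the weekly standards, under which both days before testing could be missed.

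The size of the effect is unknown. The 29%, 52% and 5% figures show only that the weekly standard does not protect the last two days. They rest on random placement of missed days and say nothing about how many children are affected. The sample size of 58 and the 81% power stand.

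The drug-return point is secondary. It touches only the Week 12 data and models that use them, not the Week 8 primary change. It also depends on families dosing after the course has ended, for which the documents give no rate. The correction is worth making because it costs little and sits next to the primary assessment.

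**What to change.** In COMPLIANCE AND SAFETY MONITORING:

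- Attach the two-day requirement and the 3-4 day rescheduling to Visit 3 (End Intervention, Week 8), including PANESS and TMS, in place of the final study visit and pTMS assessment.
- Refer to the 8-week treatment period in place of each treatment block.
- State that study drug continues until any rescheduled Visit 3 and that none is taken after it. Confirm that the dispensed kit covers this: up to 4 extra days is 4 x 2 = 8 doses, less whatever the child has left over.

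As a secondary improvement for the washout data:

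- Collect and count unused drug at Visit 3 instead of Visit 4, and record the date of the last dose.
- Copy the diary at Visit 3, but leave it (or the Med Log) with the family until Visit 4. The Week 10 and Week 12 checks can then confirm that no study drug was taken, and diary return remains the condition for the Visit 4 payment.
- Keep the diary or log as the source for the weekly and two-day rules, since a total count cannot show which days were missed.

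The cost is wording edits in the compliance and payment sections and a drug count at a visit that is already on site. No visit or procedure for the child is added. The Visit 4 payment condition becomes diary return alone, and total payment can stay at $175.
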